6.2 SPECIAL ASSAYS OR PROCEDURES

6.3.1 GLUCOSE TOLERANCE TEST

All participants will be asked to fast 12 hours prior to the test. In addition, we will ask participants to consume approximately 150 g of carbohydrates per day on the 3 days prior to the test to stabilize the participant's glucose response (See Appendix G for instruction sheet). We will perform a capillary blood draw by finger prick to obtain approximately 5uL of blood using a microcuvette. The blood sample will be immediately analyzed by an FDA-cleared glucose analyzer or stored in a refrigerator (below 46°F). We will be using HemoCue Glucose 201 system (HemoCue, Angelholm, Sweden).

6.3.2 MOTOR-EVOKED POTENTIALS AND TMS-EVOKED POTENTIALS

We will collect TMS-induced motor-evoked potentials (MEPs) and EEG potentials using EMG electrodes and a high-density EEG. Resting motor threshold (RMT) is determined while the target test muscle is at rest. EEG will be collected using Geodesic 400 system (EGI Inc., Eugene, OR, USA).

7 STUDY INVESTIGATIONAL PRODUCT

- Glucose solution

We will use a FDA-cleared glucose drink (Azer Scientific Inc., Morgantown, PA) contains the following ingredients: dextrose (source: corn), citric acid, artificial flavoring, sodium benzoate (0.1%), and purified water. The glucose solution is manufactured according to WHO and ADA standards, and it is produced in a FDA certified, pharmaceutical facility. The glucose drink is 10 fluid ounces (296mL), so the participants will receive 10 fluid ounces of water during the other session.

- Glucose tolerance test (GTT)

We will use the Glucose 201 system (HemoCue, Angelholm, Sweden) for measuring blood glucose level. The HemoCue Glucose 201 System is based on a glucose dehydrogenase method and consists of a small dedicated analyzer and a unique disposable microcuvette. The system combines the precision and accuracy of a central laboratory with the speed and convenience of obtaining results at the point-of-care. With just a fraction of a drop of whole blood and three simple steps, the HemoCue Glucose 201 System will produce immediate, accurate results for diagnosing or monitoring diabetes, as well as monitoring neonatal blood glucose levels.

The system has several features:

- Factory calibrated and traceable to ID GC-MS method, needs no further calibration and no coding
- Approximately 5 μ L whole blood sampling
- Sample material: Capillary, venous or arterial whole blood including neonatal blood
- Display range: Plasma equivalent values 0-444 mg/dL
- Result calculation time: 40-240 seconds

- Transcranial magnetic stimulation (TMS)

We will use the MagPro X100 system (MagVenture Inc., Alpharetta, Georgia, USA) for magnetic stimulation. The MagPro X100 is an advanced, high performance magnetic stimulator designed primarily for research purposes. It is a high-quality tool for researchers with a large choice of stimulating parameters and has stimulation rates up to 100 pps at high intensities and the possibility to combine waveforms and pulse modes.

The simulator has several features:

- 3 waveforms: Biphasic, Biphasic Burst and Monophasic.
- Selectable current direction.
- Stimulation rates up to 100 pulses per second.
- Easily connects to external equipment via programmable input/output triggers.
- System operation control via a built-in computer, eliminating the need for an external computer to set up and control the timing of stimulus sequences.

- Controllable from an external device.

7.1 SAFETY FEATURES

- GTT

According to the Hazard Communication Standard 29 CFR 1910.1200 and the Guidance for Hazard determination, chemicals that falls under the category "articles" does not apply to this standard.

"Article" means a manufactured item other than a fluid or particle:

- (i) which is formed to a specific shape or design during manufacture;
- (ii) which has end use function(s) dependent in whole or in part upon its shape or design during end use; and
- (iii) which under normal conditions of use does not release more than very small quantities, e.g., minute or trace amounts of a hazardous chemical and does not pose a physical hazard or health risk to employees. All HemoCue Microcuvettes are articles, therefore this standard is not applicable.

- TMS

In the USA federal law regulates the sale of Medical Devices through the US Food and Drug Administration (FDA). This is done to ensure safety and effectiveness. Devices which are permitted to be marketed for their intended use must either have a 510(k) or PMA clearance. The use of devices for other than their FDA cleared intended use is considered as investigational. Such use is only permitted if the Investigational Device Exemption (IDE) guidelines have been followed. All investigational devices must be labeled in accordance with the labeling provisions of the IDE regulation (§ 812.5) and must bear a label with this statement:

7.2 PREPARATION AND ADMINISTRATION OF STUDY INVESTIGATIONAL PRODUCT

After participants have completed the questionnaire, they will be comfortably seated. The study coordinator and/or the research assistant will be thoroughly trained and have trainings documented on the glucose blood sampling and TMS device and will be present during all sessions. To monitor side effects of blood sampling and stimulation, a questionnaire will be administered after each session.

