4 BASIC STUDY DESIGN

Participants who pass an initial screening by phone are asked to attend a screening visit where consent is provided, eligibility for study participation is confirmed and demographic information is collected. Participants who are eligible to participate will then be asked to return for two study sessions after an MRI scan. Sessions will start at 8.00 am and study participants will be asked to fast for the preceding 12 hours and to consume approximately 150g of carbohydrates each day for the 3 days prior to the session. The study procedures are identical for both study visits. The order of the two sessions is equally randomized across participants.

In one visit, an oral 3-hour GTT with a 75g load of glucose will be administered. In the other visit, pure drinking water will be used. Both study visits have the following time-line:

1. Determined the target (hand area of the left precentral gyrus, left primary motor cortex) based on MR images using a TMS neuro-navigation system.
2. Fitting of an EEG electrode net.
3. Baseline EEG and MEP measurements elicited by TMS
4. Measurement of fasting blood glucose level by finger prick
5. Administration of drink (glucose drink or water, 296mL of H₂O for both drinks)
6. Capillary blood draw (finger prick) for glucose level testing and TMS-induced EEG and MEP measurements at 0, 30, 60, 120, 180 minutes after drink administration
7. Digitization of EEG electrodes on the scalp using a camera-type scanner

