8.2.1 PHYSICAL

Risk of Injury and Discomfort: Non-invasive brain stimulation has been used without any reports of serious side-effects for more than a decade and TMS has been cleared for use in the USA by the FDA. The stimulation made nothing to do with electroconvulsive therapy that applies many orders of magnitude higher stimulation current. Some participants report a scalp pain, tingling, burning, or itching on the stimulation site but no other side effects have been noted. In order to monitor these side-effects, we will be administering side effects stimulation questionnaire after each stimulation session to determine whether these effects were experienced. Research personnel present during these sessions will also check in with the participant periodically during the stimulation to see whether they are comfortable. If any side-effect occurs (rated by the participant as stronger than “moderate”) or the participant is experiencing severe discomfort, the stimulation will be immediately stopped.

Risk of Bleeding: The glucose tolerance test is a medical test in which glucose is given and blood samples taken afterward to determine how quickly it is cleared from the blood. The test is usually used to test for diabetes, insulin resistance, impaired beta cell function, and sometimes reactive hypoglycemia and acromegaly, or rarer disorders of carbohydrate metabolism. We strictly follow the medical guidelines using an FDA-cleared device and sampler and blood sampling will be immediately stopped if any unexpected bleeding occurs.

Risk of Glucose Ingestion: The risks associated with glucose ingestion in healthy participants are minimal.

The potential side effects include nausea, sweating, light-headedness, vomiting, bloating, headache, diarrhea, and constipation. Serious side effects from the test are very uncommon.

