10.1 SAFETY PARAMETERS

STIMULATION SIDE EFFECTS. The side effects listed are headache, neck pain, scalp pain, tingling, itching, ringing/buzzing noise, burning sensation, local redness, sleepiness, trouble concentrating, improved mood, worsening of mood, dizziness, flickering lights, and other (specify). Participants are also asked to rate on a 5 point likert scale how related they believe the side effects to be to stimulation (1 = no relation, 2 = remote, 3 = possible, 4 = probable, 5 = definite).

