APPENDIX A: SCHEDULE OF EVENTS

A detailed schematic describing phone screening and study visits.

Procedures	Phone Screening	On-Site Screening	Study Sessions
Provide Verbal Consent	x		
Signed Consent Form		x	
Assessment of Eligibility Criteria	x	x	
Review of Medical History	x	x	
Review of Concomitant Medications	x	x	
Behavioral and Mood Questionnaires		x	x
Glucose Drink Administration			x
Capillary blood sampling (finger prick)			x
Non-Invasive Brain Stimulation			x
Side-Effects Questionnaires			x

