APPENDIX G: FASTING INSTRUCTIONS FOR GLUCOSE TOLERANCE TEST

Preparing for the oral glucose challenge test:

For three days before the test, you should eat a diet that contains at least 150 grams of carbohydrates a day and particularly eat at least 50 grams of carbohydrates in the meal the evening before the test.

Foods that contain 15 grams of carbs include:

A small piece of fruit

1 slice of bread

1/2 cup cooked oatmeal

1/3 cup cooked pasta or rice

4 to 6 crackers

1/2 cup black beans or other starchy vegetable

1/4 large baked potato

2/3 cup nonfat yogurt

2 small cookies

1/2 cup ice cream or sherbet

6 chicken nuggets

1/2 cup of casserole

1/4 serving of medium french fries

You should have at least 3-4 servings of these at each meal for 3 days before the test. You can have more if you like. The meal before the test is the most important meal to eat plenty of carbohydrates

These are food groups and other examples of carbohydrate containing foods:

Dairy: Milk, yogurt, and ice cream

Fruit: Whole fruit and fruit juice

Grains: Bread, rice, crackers, and cereal

Legumes: Beans and other plant-based proteins

Starchy Vegetables: Potatoes and corn

Sugary Sweets: Soda, candy, cookies, cakes

You should have nothing by mouth after 10PM the night before the test except for water, which you should drink freely to ensure that you stay well hydrated. You should not smoke after 9PM. No coffee, juice or other beverages in the morning except for water.

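### No side-effect rating is planned before each session, so symptoms present on fasted arrival can be told from new ones only by the participant's own relatedness rating

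*Combined protocol and SAP*

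**What the plan says.** Three places set the timing of the side-effect form. Section 7.2 states: "To monitor side effects of blood sampling and stimulation, a questionnaire will be administered after each session". The risk section, 8.2.1 (Physical), says the same of TMS: "we will be administering side effects stimulation questionnaire after each stimulation session to determine whether these effects were experienced". Appendix A has a row "Side-Effects Questionnaires", marked under the study sessions only. It is separate from the row for mood and behaviour questionnaires and is not split into before and after.

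On the state of participants at arrival, section 4 sets an 8.00 am start and says that "study participants will be asked to fast for the preceding 12 hours". Appendix G adds: "No coffee, juice or other beverages in the morning except for water".

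The symptom list in section 10.1 includes headache and neck pain, and also "sleepiness, trouble concentrating, improved mood, worsening of mood, dizziness". The same section provides one filter: "Participants are also asked to rate on a 5 point likert scale how related they believe the side effects to be to stimulation". That scale runs from 1 (no relation) to 5 (definite). Section 8.2.1 adds a second source of information: "Research personnel present during these sessions will also check in with the participant periodically during the stimulation".

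Section 11 (Statistical Plan) contains no side-effect analysis and no rule for deciding when a reported symptom counts as an effect of the session.

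**The concern.** Several listed symptoms are ones that a person might plausibly have on a fasted, coffee-free morning. That is a judgement; the documents do not say so. If the list is first put to participants after the session, a headache brought in at 8.00 am and a headache that began under the coil produce the same entry.

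The crossover does not solve this for the procedures that the form is meant to monitor. TMS and finger pricks are given in both the glucose and the water session, so no session lacks them. A rating taken before the first pulse is the obvious same-day reference, and the plan does not collect one. By contrast, the efficacy outcomes are analysed as change from baseline (section 11.1), and the state mood scales are taken before and after the drink (section 5.1).

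What is at stake is the description of tolerability. Section 10.2.1 judges an unanticipated problem partly on frequency and on possible relation to the research. Section 11.2 presents the trial as groundwork for a future study. Symptom rates that mix arrival symptoms with session symptoms would serve both purposes less well.

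**Working it through.** **Is there a pre-session form anywhere?** Section 5.2 has participants complete questionnaires at the start and end of each session. Section 5.1 lists the study questionnaires: STAI, PANAS, the handedness inventory, BIS/BAS and IDAS. The side-effect form is not among them, and sections 7.2 and 8.2.1 both place it after the session. Section 7.2 also mentions a questionnaire finished before the participant is seated, but does not identify it as the side-effect form. The documents therefore provide no pre-session administration.

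**What else could serve as a baseline?**

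| Source | What it gives | What it leaves open |
|---|---|---|
| Relatedness rating (10.1) | Participant's opinion, 1 to 5 | Stimulation only; not the drink or blood sampling; not severity on arrival |
| Staff check-ins (8.2.1, 8.3) | Comfort and side effects during stimulation | No rating before the first pulse |
| PANAS, STAI Y-1 (5.1) | Pre-drink state mood and anxiety | Headache, neck pain, sleepiness, dizziness and trouble concentrating are not rated directly |
| IDAS at screening (5.1) | Past-week symptoms | Not the same day |

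**Size.** The plan states no side-effect rate, so there is no figure to reproduce. The following is an illustration.

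- N = 20 participants per session (sections 3 and 11.1).
- i = share in whom the session causes a given symptom. Not in the documents; assumed 10%.
- b = share with the symptom on arrival. Not in the documents; assumed 10% to 30%.
- Further assumptions: arrival and session causes are independent, every arrival symptom lasts until the form is completed, and all symptoms are reported whatever their relatedness rating.

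Reported after the session: b + (1 − b) × i. New onset: (1 − b) × i.

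| b | Reported after | Of 20 | New onset | Of 20 |
|---|---|---|---|---|
| 10% | 0.10 + 0.90 × 0.10 = 0.19 | 3.8 | 0.09 | 1.8 |
| 20% | 0.20 + 0.80 × 0.10 = 0.28 | 5.6 | 0.08 | 1.6 |
| 30% | 0.30 + 0.70 × 0.10 = 0.37 | 7.4 | 0.07 | 1.4 |

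The gap between reported and new onset is always b: 2, 4 or 6 of 20. It does not depend on i. With i = 5%, 2.9 to 6.7 of 20 report the symptom and 0.9 to 0.7 are new. With i = 20%, 5.6 to 8.8 report it and 3.6 to 2.8 are new.

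New onset falls a little short of the 2 of 20 caused by the session (20 × 0.10), because b × i of participants have both causes: 0.2 of 20 at b = 10% and 0.6 at b = 30%. A count of symptoms that are new or stronger recovers these if each is recorded as stronger: 1.8 + 0.2 = 2.0 and 1.4 + 0.6 = 2.0.

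**Glucose against water.** If both sessions share the same b, the difference in reported rates is (1 − b) times the true difference. A true 10-point difference (20% against 10%) shows as 9, 8 or 7 points at b = 10%, 20% or 30%. Most of the shared background cancels.

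**The case against.** The strongest reply is that the plan never says that arrival symptoms are attributed to the session. A reader might infer that from the post-session timing, but the documents do not support it. There is no counting rule, and a participant with a fasting headache can mark it as unrelated to stimulation. This stands. What remains is that nothing except the participant's opinion separates the two kinds of symptom, and that opinion is asked about stimulation only.

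A reader might also infer that a glucose-water comparison of side effects is distorted. No such comparison is planned for this form; sections 5.1 and 11.1 plan between-session comparisons only for the mood and motivation scales. A shared background would also largely cancel, so this is no main argument for the change.

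Other parts of the reply also stand:

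- The rates above are assumed and need arrival symptoms to persist for more than three hours.
- A pre-session form does not remove all effects of fasting. In the water session the fast continues to the 180-minute measurement, and hunger or lack of coffee could produce symptoms that look new.
- The mood items have a partial baseline in PANAS and STAI Y-1.
- The side-effect form is not among those reproduced in Appendix F. If it asks when each symptom began, part of the gap closes.
- Over-reporting is the cautious direction for safety monitoring, and side effects are not a study outcome.

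These points limit the concern without answering it. Headache, neck pain, sleepiness, dizziness and trouble concentrating still have no planned same-day reference.

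**Conclusion.** The gap is real but narrow. As written, the plan cannot separate symptoms present on arrival from those that began in the session, except through a self-rated opinion about stimulation. The water session does not help for TMS or finger pricks.

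Under the assumed rates (10% session incidence, 10% to 30% present on arrival, independent and persisting), 3.8 to 7.4 of 20 would report a symptom and 1.8 to 1.4 would be new onset. The size rests wholly on these assumptions, since the documents give no rates. That fasting and missing coffee produce listed symptoms is likewise a judgement.

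The consequence is confined to how side effects are described. Sample size, power and the primary analysis do not change. This is a cheap improvement to safety measurement, not a flaw that threatens the main result.

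**What to change.** In sections 7.2, 8.2.1 and 10.1, state that the same symptom list is completed before the first TMS pulse of each session, including the pulses used to find the motor threshold, and again after the session. Mark both times in Appendix A. Report all post-session symptoms, and report separately those that are new or stronger than on arrival, alongside the relatedness rating. Keeping the full list means that no reported symptom is dropped.

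The cost is 20 × 2 = 40 extra short forms, a little participant time and a wording amendment. Symptoms that develop during the session from the continuing fast would remain unseparated, and the report should say so. The change has to be made before sessions run, because arrival symptoms cannot be recovered reliably afterwards.

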7.3 ASSESSMENT OF PARTICIPANT COMPLIANCE WITH STUDY INVESTIGATIONAL PRODUCT

Compliance for this study includes making 2 study sessions. Participants have the ability to schedule their second visit 3 days after the first visit. Follow-up emails will be sent out 1 day before the scheduled second visit.

8 POTENTIAL RISKS AND BENEFITS

8.1 BENEFITS TO SUBJECTS AND SOCIETY

There is no direct benefit to participants but the research outcome will help to design new study for understanding the underlying mechanism of brain network excitability and diabetes.

8.2 POTENTIAL RISKS

8.2.1 PSYCHOLOGICAL

Risk of Embarrassment: Self-report questionnaire contains questions regarding personal information. This risk is necessary in order to assess symptomology and associated psychopathology. Participants will be assured upon intake that only study personnel will see any answers.

Risk of Confidentiality Breach. To avoid breaches in confidentiality, study documents that contain personal information, including the informed consent, and the document that links study ID numbers to personal identifying information are kept in locked filing cabinets in locked rooms, separate from any source documents containing participating dummy identifiers. All data is stored in locked cabinets inside locked offices; electronic data will be stored only on password-protected computers, and data encryption methods will be used during communication between investigators. Only study personnel will have access to these data. All study staff participate in annual human participating training that includes education about responsibilities to minimize the risk of confidentiality breach. In the unlikely event of a breach of confidentiality, people might discover that an individual was involved in this research study and some people might not agree with the principle of participating in research or of changing natural brain activity.

8.2.1 PHYSICAL

Risk of Injury and Discomfort: Non-invasive brain stimulation has been used without any reports of serious side-effects for more than a decade and TMS has been cleared for use in the USA by the FDA. The stimulation made nothing to do with electroconvulsive therapy that applies many orders of magnitude higher stimulation current. Some participants report a scalp pain, tingling, burning, or itching on the stimulation site but no other side effects have been noted. In order to monitor these side-effects, we will be administering side effects stimulation questionnaire after each stimulation session to determine whether these effects were experienced. Research personnel present during these sessions will also check in with the participant periodically during the stimulation to see whether they are comfortable. If any side-effect occurs (rated by the participant as stronger than “moderate”) or the participant is experiencing severe discomfort, the stimulation will be immediately stopped.

Risk of Bleeding: The glucose tolerance test is a medical test in which glucose is given and blood samples taken afterward to determine how quickly it is cleared from the blood. The test is usually used to test for diabetes, insulin resistance, impaired beta cell function, and sometimes reactive hypoglycemia and acromegaly, or rarer disorders of carbohydrate metabolism. We strictly follow the medical guidelines using an FDA-cleared device and sampler and blood sampling will be immediately stopped if any unexpected bleeding occurs.

Risk of Glucose Ingestion: The risks associated with glucose ingestion in healthy participants are minimal.

The potential side effects include nausea, sweating, light-headedness, vomiting, bloating, headache, diarrhea, and constipation. Serious side effects from the test are very uncommon.

